### 8.2.7 Cerebrospinal Fluid Safety Lab

A CSF safety laboratory sample obtained at the times noted on the Schedule of Assessments (Table 1, Table 2, and Table 3) will be evaluated at a local lab. The following parameters will be assessed: total protein, glucose, and cell counts (white blood cell counts with differential).

Samples will only be used by the Sponsor and/or a contracted vendor for research related to the development of treatments for HD and stored for a maximum of 10 years. All biological material will be stored and secured in a way that ensures that unauthorized access is prohibited and the samples are not lost, deteriorated, or destroyed accidentally or illegally. Detailed instructions for sample collection, storage, processing, and shipping will be provided in the Laboratory Manual.

### **8.2.8 Suicidality Assessment (Columbia-Suicide Severity Rating Scale)**

The C-SSRS is a measure of suicidal ideations and suicidal behaviors. The C-SSRS, provided in Appendix 2, consists of 2 forms: a form measuring symptoms at Screening (baseline/screening version) that includes a lifetime history, and a form measuring symptoms since the last study visit ('since last visit' version). The baseline/screening form will be performed at the Screening visit, and the 'since last visit' form will be performed at all later time points, as described in the Schedule of Assessments (Table 1, Table 2, and Table 3). A trained rater will complete this scale. The findings should be confirmed by the clinical opinion of the Investigator.

The Investigator should be notified if a patient responds "yes" to any of the questions. The Investigator will provide care according to local standards, which may include referral to specialists, medical treatment, or hospitalization as necessary.

### **8.2.9 Pregnancy Testing**

For female patients of childbearing potential, a negative serum pregnancy test must be documented at the Screening Visit and a negative urine pregnancy test must be documented at the times noted on the Schedule of Assessments (Table 1, Table 2, and Table 3). The serum pregnancy test will be determined by a central lab; urine pregnancy tests will be performed locally.

### **8.2.10 Drug Screening**

A urine drug screen for opioids, cocaine, amphetamines, methadone, barbiturates, methamphetamine, and phencyclidine will be performed at the times noted on the Schedule of Assessments (Table 1, Table 2, and Table 3). Drug screen tests will be evaluated by a central laboratory.

## **8.3 PHARMACOKINETIC ASSESSMENTS**

Cerebrospinal fluid as well as plasma and urine samples for analysis of exposure to WVE-120101 will be collected at the time points specified on Schedule of Assessments (Table 1, Table 2, and Table 3). The date and time of the sample collection will be recorded.

Samples will be analyzed by a central laboratory to determine concentrations of WVE-120101 using a validated method.

Samples will only be used by the Sponsor and/or a contracted vendor for research related to the development of treatments for HD and stored for a maximum of 10 years. All biological material will be stored and secured in a way that ensures that unauthorized access is prohibited

and the samples are not lost, deteriorated, or destroyed accidentally or illegally. Detailed instructions for sample collection, storage, processing, and shipping will be provided in the Laboratory Manual.

## 8.4 PHARMACODYNAMIC ASSESSMENTS

A CSF sample will be collected at the time points noted in the Schedule of Assessments (Table 1, Table 2, and Table 3) to determine the change from baseline in concentration of mHTT protein. In addition, exploratory biomarkers (e.g., neurofilament light and total tau) may be assessed.

The study may utilize the method described in Wild et al or an alternative method to determine levels of mHTT protein. Following unblinding, the study randomization will be provided to the bioanalytical laboratory to enable analysis of the PD samples.

Samples will only be used by the Sponsor and/or a contracted vendor for research related to the development of treatments for HD and stored for a maximum of 10 years. All biological material will be stored and secured in a way that ensures that unauthorized access is prohibited and the samples are not lost, deteriorated, or destroyed accidentally or illegally. Detailed instructions for sample collection, storage, processing, and shipping will be provided in the Laboratory Manual.

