## **7 BLINDING**

### **7.1 BLINDING AND RANDOMIZATION**

This is a double-blind and placebo-controlled randomized study. The treatment blind will not be broken until the end of the study, except in the case of emergency ([Section 7.2](#)). The Sponsor and contract research organization (CRO) staff directly responsible for the conduct of data collection for the study, the Investigator, and study center staff will be blinded to treatment for the duration of the study until such time that all discrepancies in the clinical database are resolved (ie, at the time of the database lock).

The randomization scheme will be assigned by an IXRS, which will send notifications of the treatment assignment to the designated pharmacy personnel.

The pharmacy personnel will be unblinded to prepare doses of WVE-120101 or placebo to ensure that the clinical site staff responsible for administering study drug and conducting assessments per the protocol, and the patient, remain blinded to study treatment. In addition, a clinical research associate will be unblinded to perform drug vial accountability and oversee the shipping and inventory of study drug.

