## 8.5 Immunogenicity Assessments

Serum samples will be collected at the times noted on the Schedule of Assessments (Table 1 and Table 2) and analyzed at a central laboratory for measurement of anti-drug antibodies to WVE-120101.

All biological material will be stored and secured in a way that ensures that unauthorized access is prohibited and the samples are not lost, deteriorated, or destroyed accidentally or illegally. Detailed instructions for sample collection, storage, processing, and shipping will be provided in the Laboratory Manual.

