### 10.3.4 Protocol Deviations

Assessment of protocol deviations as ‘minor’ or ‘major’ will be determined blinded to treatment and prior to database unblinding. A protocol deviations log will be finalized before unblinding and final database lock. Protocol deviations will be presented by patient in a data listing.

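### Section 8.4 releases the randomisation to the bioanalytical laboratory for analysis of the PD samples, and nothing in the documents says the mHTT assay is masked

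*Combined protocol and SAP*

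**What the plan says.** Section 8.4 (Pharmacodynamic Assessments) provides for CSF samples to be assayed for mHTT by a published method or an alternative one. It then states: "Following unblinding, the study randomization will be provided to the bioanalytical laboratory to enable analysis of the PD samples". It does not say which unblinding is meant, why the laboratory needs the codes, or whether assay staff are masked when they measure.

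Section 7.1 (Blinding and Randomization) gives the general rule: "The treatment blind will not be broken until the end of the study, except in the case of emergency". It names the people who stay blinded, among them Sponsor and CRO "staff directly responsible for the conduct of data collection for the study, the Investigator, and study center staff will be blinded to treatment", in their case until database lock; the patient is also to remain blinded. It names two unblinded roles: "The pharmacy personnel will be unblinded to prepare doses of WVE-120101 or placebo", and "a clinical research associate will be unblinded to perform drug vial accountability". The bioanalytical laboratory is not named in either group.

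Section 10.10 (Interim Analyses) allows administrative analyses that include mHTT, with unblinded summaries by treatment group, under a Data Access Plan. It sets no time for them.

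mHTT in CSF is a secondary endpoint (Section 3.2). Section 10.5 summarises it by dose cohort and visit, with change from baseline to the last measured time point.

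**The concern.** Section 8.4 lays down a sequence: unblinding, then codes to the laboratory, then analysis of the samples. If analysis means the measurement, the people running the assay can see which samples are active and which are placebo.

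A quantitative assay still involves judgement, for example whether to repeat a sample, accept a run, or how to treat a low value. If those decisions are made with the codes in view, they can depend on treatment and feed into the mHTT change from baseline. The plan leaves the mHTT method open, so the documents do not show how much discretion the assay involves. A later reader of the results could not rule out this influence from the protocol, and short of re-assay it could not be undone.

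**Working it through.** No arithmetic applies. The plan gives no figure for assay masking. Its one mHTT figure, a 90% confidence interval of about ±110 fM with 9 patients per active dose (Section 10.2), concerns precision and cannot size a bias. The check is therefore of the text.

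**Step 1. What does *analysis* mean in 8.4?** The neighbouring laboratory sections use the verb for the measurement. Section 8.3: "Samples will be analyzed by a central laboratory to determine concentrations of WVE-120101 using a validated method". Section 8.5: serum samples are "analyzed at a central laboratory for measurement of anti-drug antibodies". In 8.4 the object is the samples and the recipient is a laboratory, which fits the same meaning. Against this, 8.4 uses other verbs for its own measurements, and Sections 10.3.1 and 10.5 use PD analysis for the statistical summaries. The possible readings are:

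| Reading of *analysis* | Does the laboratory hold codes during measurement? |
|---|---|
| Measuring mHTT | Yes |
| Selecting or laying out samples before the assay | Possibly, if the same staff then run the assay |
| Handling results after they are final | No |

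The first is the natural reading, but the text does not exclude the others.

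**Step 2. When are the codes released?** Section 7.1 offers two dates: the end of the study and, for the named staff, database lock. Section 14.3 defines the end of the study as the last patient's last visit, which is a different event from lock. Section 10.3.4 mentions unblinding alongside final lock but does not define it. An administrative analysis under 10.10 that took place before lock would need mHTT results earlier still, and the documents do not say whether the laboratory would then hold codes. Section 8.4 refers to none of these sections.

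**Step 3. Would a late date settle it?** No. If the samples are measured after codes are released, waiting until lock protects site and data staff but leaves the assay unmasked. What matters is whether results are final before the laboratory receives the codes, and that order is not stated.

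**Step 4. Is masking stated elsewhere?** The statements on blinding, unblinding, the PD laboratory and interim access do not say that mHTT samples are coded, that assay staff are masked, or that results are finalised before release. The plan does state masking for another task: classification of protocol deviations "will be determined blinded to treatment and prior to database unblinding" (Section 10.3.4).

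**The case against.** The strongest reply has five parts.

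- **Unblinding has a default meaning.** A reader might infer from 8.4 alone that the term is undefined. That goes too far, because 7.1 supplies a default and 10.3.4 pairs unblinding with lock. What remains is that 8.4 does not point to that default, that two dates are possible, and that 10.10 adds a third route to unblinded mHTT data.
- **The word analysis is not settled.** This stands. The concern rests on the natural reading, not the only one.
- **Other documents may cover it.** This also stands. Run acceptance and repeat rules commonly sit in laboratory documents, and silence in the protocol does not prove an unmasked assay. But 8.4 describes the Laboratory Manual as covering collection, storage, processing and shipping. A manual that masked the assay would sit awkwardly beside the 8.4 sentence, which would still need correction.
- **The laboratory may already be covered by 7.1.** A contracted laboratory might count as CRO staff responsible for data collection. That is unclear. Even if it does, 7.1 protects the blind only up to lock, and 8.4 releases the codes following unblinding.
- **The stakes are limited.** Safety is primary, the analyses are mainly descriptive, and the sample size was not based on a hypothesis test. This is fair, and it limits the weight of the point. It does not remove the reason to mask a secondary endpoint when masking costs little.

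**Conclusion.** The point holds in limited form. Section 8.4 affirmatively sends the randomisation to the laboratory for analysis of the PD samples. On the natural reading this permits an unmasked mHTT assay, and no safeguard is stated in the documents reviewed. The time of release cannot be fixed from 7.1, 10.10 and 14.3.

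The size of any bias cannot be estimated. The conclusion assumes that analysis includes the measurement and that the unseen Laboratory Manual, Data Access Plan and separate SAP do not already mask the assay. Confidence is medium for those reasons. The primary safety endpoint is unaffected.

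Two stronger inferences are not supported. A reader might infer that 8.4 contradicts 7.1. It does not by itself: the laboratory is not named there, and release is placed after unblinding. A reader might also infer that mHTT results will be biased, or that the assay will certainly be run with codes in view. The documents show only that masking is not stated. Section 10.10 matters here solely because it leaves the release point open; no change to it or to 7.1 is proposed.

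**What to change.** Replace the sentence in Section 8.4 with:

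> mHTT assays, including any used for the Section 10.10 administrative analyses, will be run on coded samples, and results finalised and transferred, by laboratory staff masked to treatment; treatment codes will be released to the laboratory only afterwards, if at all. If codes are needed for sample selection or plate layout, a person already unblinded and outside the assay team will apply them.

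This makes the calendar date of unblinding unimportant for the assay, because release is tied to final results. It also accommodates the benign reading: if the laboratory needs codes only to choose or arrange samples, that can still be done.

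The cost is one sentence in the protocol and matching laboratory instructions. The downside is a small layout task for someone already unblinded, and only if codes are needed. The documents do not say why the laboratory needs the codes, so the sponsor should confirm that this arrangement meets the purpose.

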## 8.5 Immunogenicity Assessments

Serum samples will be collected at the times noted on the Schedule of Assessments (Table 1 and Table 2) and analyzed at a central laboratory for measurement of anti-drug antibodies to WVE-120101.

All biological material will be stored and secured in a way that ensures that unauthorized access is prohibited and the samples are not lost, deteriorated, or destroyed accidentally or illegally. Detailed instructions for sample collection, storage, processing, and shipping will be provided in the Laboratory Manual.

## 8.6 MAGNETIC RESONANCE IMAGING

A 3 Tesla (3T) MRI of the whole brain (without contrast) will be performed at the time points noted on the Schedule of Assessments (Table 1, Table 2, and Table 3). Sedation is permitted during the MRI.

The MRI will be assessed for safety purposes, in addition to exploratory structural assessments. Exploratory assessments will include, but are not limited to, volumetric assessments. Changes in MRIs of the brain will be characterized in patients receiving WVE-120101.

The MRI will be performed by an appropriately trained individual. Detailed instructions on how the MRI will be performed and transferred to the central reader are provided in the Imaging Manual. The scans will be evaluated by a central reader.

## 8.7 ASSESSMENT OF CLINICAL EFFECTS

### 8.7.1 Unified Huntington's Disease Rating Scale

The UHDRS is a research tool developed by the Huntington Study Group to provide a uniform assessment of the clinical features and course of HD. The scale consists of 6 subtests, including motor assessment, cognitive assessment, behavioral assessment, an independence scale, functional assessment, and TFC, and is provided in [Appendix 1](#). All subtests of the UHDRS should be performed except the behavioral assessment, as the PBA-s ([Section 8.7.2](#)) collects similar behavioral information.

The motor assessment evaluates motor features of HD with standardized ratings of oculomotor function, dysarthria, chorea, dystonia, gait, and postural stability. The total motor impairment score is the sum of all the individual motor ratings, with higher scores indicating more severe motor impairment than lower scores.

The cognitive assessment consists of a lexical verbal fluency test, Symbol Digit Modalities Test (SDMT), and the Stroop Interference test. The Stroop Test results are reported as the raw number of correct answers given in a 45-second period. Results for the other tests are reported as the raw number of correct responses. Higher scores indicate better cognitive performance.

The independence scale is used to follow disease progression in functional disability. The scale is rated from 100 (no special care needed) to 0 (tube-fed, total bed care).

The functional assessment checklist is a 25-question assessment that screens for capacity to complete the tasks mentioned in the assessment alone. The questions are asked in the presence of a family or friend to get the clinician's best judgment based on both responses. A response of "yes" is given a score of 1. A high score indicates better functioning.

The TFC is a brief interview involving the patient and a close family member or friend familiar with the patient's functioning. The measure has 5 items and addresses basic activities of living: occupation, handling finances, domestic responsibilities, activities of daily living (eg, eating, dressing, bathing), and level of care.

The change from baseline to the last measured time point will be determined.

### 8.7.2 Short Problem Behaviors Assessment

The PBA-s is a shorter version of the Problem Behaviors Assessment for HD (PBA-HD), a semi-structured interview designed to elicit information about behavioral symptoms relevant to HD. The shorter version was developed by the Behavioral Phenotype Working Group of the European Huntington's Disease Network (EHDN).

The PBA-s contains 11 items, each measuring a different behavioral problem that is rated for both severity and frequency on a 5-point scale. Severity and frequency ratings are multiplied to provide an overall score for each symptom. The PBA-s is provided in [Appendix 3](#).

Interviews are conducted with the patient. The final rating is determined by assessing all available information, including the interviewer's own observations of the patient's behavior. A caregiver should not be interviewed as part of the PBA-s for this study.

The change from baseline to the last measured time point will be determined.

## **9 ADVERSE EVENTS**

The Investigator is responsible for reporting all AEs that are observed or reported during the study, regardless of their relationship to study treatment or their clinical significance.

Adverse events will be assessed beginning at enrollment (date of signed informed consent) and up to the end of the study.

An AE is defined as any untoward medical occurrence in a patient enrolled into this study regardless of its causal relationship to study treatment. Patients will be instructed to contact the Investigator at any time after randomization if any symptoms develop.

A TEAE is defined as any event not present before exposure to study treatment or any event already present that worsens in either intensity or frequency after exposure to study treatment (excluding worsening of results on the UHDRS or PBA-s rating scales).

### **9.1 ELICITING AND DOCUMENTING ADVERSE EVENTS**

All AEs reported or observed during the study, including AEs resulting from concurrent illnesses, reactions to concurrent medications, or progression of disease states, will be recorded on the AE page in the eCRF and in the site source notes. The eCRFs used to document AEs are designed to help ensure this information is collected in a standard manner. Information to be collected includes event term, date and time of onset, date and time of resolution, Investigator-specified assessment of severity and relationship to study treatment, action taken with respect to study treatment, seriousness, any required treatment or evaluations, and outcome. All AEs will be followed to adequate resolution. The sites will be provided completion guidelines for the eCRF, which will further guide them on how to record the data, including AEs. The MedDRA will be used to code all AEs.

Any medical condition that is present at the time that the patient is screened but does not worsen should not be reported as an AE. However, if it worsens at any time during the study, this should be recorded as an AE. This includes any spontaneously reported worsening of depression (ie, not based on the study rating scales).

In addition to observations of the patient, AEs identified from any study data (eg, laboratory values, physical examination findings, ECG changes, C-SSRS) or identified from review of other documents that are considered clinically significant will be documented on the AE page in the eCRF. The eCRFs also include a form specifically for a detailed neurological assessment, with instructions to report any worsening as an AE. Worsening of symptoms that are only detected on clinical effects rating scales will not be reported as AEs.

Adverse events (AEs) will be solicited at each visit by direct questioning as well as elicited from physical and neurological examination by site staff. In addition, all sites in the study must ensure patients have a 24-hour telephone number to contact medical site staff for the duration of the study, in case of emergent AEs or SAEs.

If there is any doubt as to whether a clinical observation is an AE, the event should be reported. Adverse events characterized as intermittent do not require documentation of onset and duration of each episode.

Pregnancy is not considered an AE. However, if a patient becomes pregnant during the course of the study, the pregnancy must be reported and monitored as described in [Section 9.5](#).

## 9.2 DEFINITIONS OF ADVERSE EVENT SEVERITY AND RELATIONSHIP TO STUDY DRUG

### 9.2.1 Severity

The severity, or intensity, of an AE refers to the extent to which an AE affects the patient's daily activities. Adverse event severity will be evaluated using the NCI CTCAE version 4.0, published 28 May 2009. For AEs not included in the NCI CTCAE, the Investigator will be required to assess the intensity of the adverse drug/biologic experience using the criteria in [Table 6](#).

**Table 6** Definitions of AE Severity Using NCI CTCAE Criteria

Grade	AE Severity	Definition
1	Mild	Mild; asymptomatic or mild symptoms; clinical or diagnostic observations only; intervention not indicated.
2	Moderate	Moderate; minimal, local or noninvasive intervention indicated.
3	Severe	Severe or medically significant but not immediately life-threatening; hospitalization or prolongation of hospitalization indicated; disabling; limiting self care.
4	Life threatening	Life-threatening consequences; urgent intervention indicated.
5	Death	Death related to AE.

Abbreviations: AE = adverse event; CTCAE = Common Terminology Criteria for Adverse Events; NCI = National Cancer Institute.

Changes in the severity of an AE should be documented in the eCRF to allow an assessment to be performed of the duration of the event at each level of intensity.

